5.3.2.2 Secondary endpoints

The secondary efficacy endpoints are related to the evolution of serologic and viral markers as well as the PBMC ELISpot by days 85 and 169.

The secondary endpoints will be considered as described in section 4.2.2. Analyses to be performed are described in the following subsections.

No multiplicity adjustments will be made for secondary endpoints.

5.3.2.2.1 Proportion of patients achieving serologic clearance of HBsAg on Day 169

Patients who discontinue early or have missing HBsAg values on Day 169 but who achieve serologic clearance of HBsAg on the last available assessment prior to Day 169 will be treated as responders for this endpoint; otherwise, patients with early discontinuation or missing HBsAg values on Day 169 will be treated as non-responders.

The proportion of patients achieving serologic clearance of HBsAg on Day 169 will be estimated as follows:

(Number of patients having achieved serologic clearance of HBsAg on Day 169) / (Number of patients in the corresponding treatment (or overall)) x 100%

This proportion will be compared between treatment groups using Chi-Squared Test or Fisher's Exact Test at a 0.05% two-sided level of significance. Fisher's Exact Test will be used if the expected values of at least the 80% of the cells in the contingency table created for estimating proportions are lower than 5.

This proportion will be analyzed using logistic regression models with treatment group and baseline qHBsAg level as covariate. The analysis of maximum likelihood and odds ratio estimates for patients predicting a 'Yes' in achieving serologic clearance of HBsAg on Day 169 will be shown.

5.3.2.2.2 Proportion of patients achieving serologic clearance of HBV DNA on Day 169

Patients who discontinue early or have missing HBV DNA values on Day 169 but who achieve serologic clearance of HBV DNA on the last available assessment prior to Day 169 will be treated as responders for this endpoint; otherwise, patients with early discontinuation or missing HBV DNA values on Day 169 will be treated as non-responders.

The proportion of patients achieving serologic clearance of HBV DNA on Day 169 will be estimated as follows:

(Number of patients having achieved serologic clearance of HBV DNA on Day 169) / (Number of patients in the corresponding treatment (or overall)) x 100%

This proportion will be compared between treatment groups using Chi-Squared Test or Fisher's Exact Test at a 0.05% two-sided level of significance. Fisher's Exact Test will be used if the expected values of at least the 80% of the cells in the contingency table created for estimating proportions are lower than 5.

This proportion will be analyzed using logistic regression models with treatment group and baseline HBV DNA levels as covariate. The analysis of maximum likelihood and odds ratio estimates for patients predicting a 'Yes' in achieving serologic clearance of HBV DNA on Day 169 will be shown.

5.3.2.2.3 Changes in qHBsAg, HBV DNA, HBcrAg and pg-RNA levels, Baseline to Days 85 and 169

Changes from baseline to days 85 and 169 in qHBsAg, HBV DNA (and HBV DNA log), HBcrAg (Log U/mL and kU/mL) and pg-RNA will be summarized by means of descriptive statistics including mean, standard deviation, median, Q1 and Q3, minimum and maximum by treatment arm.

Changes from baseline for qHBsAg levels will be analyzed fitting a mixed model for repeated measures (MMRM) including treatment group, visits days (Day 1 through Day 169), and baseline values as a covariate. Interactions between visit days and treatment group will also be included. The model will employ an unstructured within patient covariance matrix and a restricted maximum likelihood (ReML) estimation method. In addition, HBV DNA, HBcrAg and pg-RNA will be analyzed in the same manner. The data distribution will be tested for normality and appropriate transformations will be applied, as needed. Any transformation, if applied, will be reported.

Change from baseline is calculated only for patients with non-missing values for both the baseline and the time-point of interest and will be missing otherwise.

5.3.2.2.4 Change in IFN-γ frequency by ELISpot assay in PBMCs, Baseline to Days 85 and 169

Changes from Day 1 to days 85 and 169 in IFN-γ frequency by ELISpot assay in PBMCs (including LPMIX9 IFN-γ SFC and will be summarized by means of descriptive statistics including mean, standard deviation, median, Q1 and Q3, minimum and maximum by treatment arm.

Changes from baseline for IFN- γ frequency by ELISpot assay in PBMCs levels (including LPMIX9 IFN- γ SFC a) will also be analyzed fitting a mixed model for repeated measures (MMRM) including treatment group, visits days (Day 1 through Day 169), and baseline values as a covariate. Interactions between visit days and treatment group will also be included. The model will employ an unstructured within patient covariance matrix and a restricted maximum likelihood (ReML) estimation method. The data distribution will be tested for normality and appropriate transformations will be applied, as needed. Any transformation, if applied, will be reported.

Change from baseline is calculated only for patients with non-missing values for both the baseline and the time-point of interest and will be missing otherwise.

- The LPMIX9 variable is not normally distributed, and none of the transformations we have attempted are valid.
 - Upon examining the data, highly right-skewed distribution was observed, with a significant number of subjects reporting a value of 0.
 - Given these challenges we cannot proceed the Mixed model proposed the previous version of SAP because the data do not fit the assumptions of normality. Therefore, the Wilcoxon-Mann Whitney test to compare these differences between treatments will be used instead.

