6.2. Randomization

Following completion of the Screening activities, patients who meet the all the inclusion and none of the exclusion criteria will be registered by the Interactive Web Response System (IWRS). Eligible patients will be randomly assigned in a 1:1 ratio to HepTcell or placebo treatment groups. Randomization will be stratified by study center to minimize imbalances between treatment groups.

The first 12 patients (6 HepTcell, 6 placebo) will form the sentinel cohort. To assure a 1:1 distribution of HepTcell and placebo in the sentinel cohort, randomization in this group will not be stratified.

If none of the Stopping Rules (see Section 7.1.1) are met in one or more patients in the sentinel cohort, randomization may continue in the expanded study cohort.

The randomization list will be drawn up by an independent statistician.

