10.4. Statistical Methods

10.4.1. Primary Efficacy Endpoint

For the primary analysis, proportions of patients with virologic response, defined as a 1.0-log reduction in HBsAg or serologic clearance of HBsAg, will be compared between HepTcell and placebo groups using Fisher's Exact Test at a 0.05% two-sided level of significance.

Patients who discontinue prematurely or have missing data will be considered nonresponders for that endpoint. Linear and logistic regression will be employed to examine the effects of baseline factors, such as qHBsAg level, HBV DNA levels, and hepatitis B genotype on response.

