10.4.2. Secondary and Exploratory Efficacy Endpoints

The same approach as used for the primary efficacy endpoint will be applied for secondary and exploratory endpoints that are categorical in nature.

Changes from baseline in PBMC ELISpot, HBsAg, HBcrAg, pg-RNA, and quantitative HBV DNA will be analyzed using a mixed model for repeated measures (MMRM). The model will include the fixed effects of treatment, stratification factor, week, and treatment-by-visit interaction as well as the continuous, covariate of baseline level. The model will employ an unstructured within patient covariance matrix and a restricted maximum likelihood (ReML) estimation method.

Relationships between hepatitis flares and HBsAg loss and/or decline will be evaluated logistic and linear regression.

A Kaplan-Meier model will be developed to compare changes between treatment groups in HBsAg clearance and a 1-log reduction in HBsAg over time.

No multiplicity adjustments will be made for secondary or exploratory endpoints.

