5.3.2.1 Primary endpoint

The primary endpoint will be considered as described in section 4.2.1.

Patients who discontinue early or have missing HBsAg values on Day 169 but who achieve virologic response or serologic clearance of HBsAg on the last available assessment prior to Day 169 will be treated as responders for the primary endpoint; otherwise, patients with early discontinuation or missing HBsAg values on Day 169 will be treated as non-responders.

The proportion of patients achieving virologic response (defined as a 1.0-log reduction in HBsAg or serologic clearance of HBsAg) on Day 169 will be estimated as follows:

(Number of patients having achieved virologic response or serologic clearance of HBsAg to Day 169) / (Number of patients in the corresponding treatment (or overall)) x 100%

This proportion will be compared between treatment groups using Chi-Square Test or Fisher's Exact Test at a 0.05% two-sided level of significance. Fisher's Exact Test will be used if the expected values of at least the 80% of the cells in the contingency table created for estimating proportions are lower than 5.

This proportion will be analyzed using logistic regression models with treatment arm and baseline qHBsAg level as covariate. The analysis of maximum likelihood and odds ratio estimates for patients predicting a 'Yes' in achieving virologic response will be shown.

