5.3.17 Changes to Protocol-planned Analyses

According to the protocol, ECG parameters will be summarized by treatment group and protocol specified collection time point and a summary of change from baseline at each protocol specified time point by treatment group will also be presented. However, ECG parameters have not been collected and they are not available for analyses.

22-Apr-2024

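### The SAP leaves study centre out of the viral-marker MMRMs and drops the protocol's linear regressions on baseline factors and on flares, without listing these changes in 5.3.17

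*SAP*

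**What the plan says.** **Centre.** Protocol 6.2 states: "Randomization will be stratified by study center to minimize imbalances between treatment groups". The 12 sentinel patients are exempt. Protocol 10.4.2 carries this into the analysis of change from baseline: "The model will include the fixed effects of treatment, stratification factor, week, and treatment-by-visit interaction", with baseline level as covariate. SAP 5.3.2.2.3 gives the model for qHBsAg, HBV DNA, HBcrAg and pg-RNA as "including treatment group, visits days (Day 1 through Day 169), and baseline values as a covariate", plus the interaction. No SAP model contains centre or region.

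**Baseline factors.** Protocol 10.4.1 plans linear and logistic regression "to examine the effects of baseline factors, such as qHBsAg level, HBV DNA levels, and hepatitis B genotype on response". SAP 5.3.2.1 specifies "logistic regression models with treatment arm and baseline qHBsAg level as covariate", and 5.3.2.2.1 does the same for HBsAg clearance. Baseline HBV DNA enters only the logistic model for HBV DNA clearance (5.3.2.2.2). Genotype is summarised descriptively (5.3.1.3) and enters no model.

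**Flares.** Protocol 10.4.2: "Relationships between hepatitis flares and HBsAg loss and/or decline will be evaluated logistic and linear regression". SAP 5.3.3.14 keeps only a logistic model of HBsAg loss, defined as at least two consecutive negative results. The table index lists nothing further.

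**Declared changes.** SAP 5.3.17 has one entry, which begins "According to the protocol, ECG parameters will be summarized by treatment group". The version 2.0 history line mentions the non-parametric model, minor issues and the modified table list.

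**The concern.** The protocol says the SAP will specify all statistical methods (10.6), so an analysis absent from the SAP has in effect been dropped. A reader who relies on 5.3.17 would think that only the ECG summaries had changed.

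Three things are at stake. The first is precision in the marker comparisons, because the design stratified on a factor that the model ignores. The second is the protocol's question of who responds. Without HBV DNA, genotype or a linear model it rests on a binary outcome with few expected events. The third is whether flares go with HBsAg decline. The retained analysis needs confirmed HBsAg loss, which is much rarer than decline.

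**Working it through.** **1. The plan's own figure.** Protocol 10.2 assumes 3% response on placebo and 25% on HepTcell, 40 per arm, two-sided 0.05, and states about 80% power. Enumerating all outcomes under Fisher's exact test gives 78.0%, which agrees. This point does not depend on the power, but it uses the same rates.

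**2. Term by term.**

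| Protocol element | In the SAP? |
|---|---|
| Centre in the MMRM, four viral markers | No |
| MMRM for ELISpot | Openly replaced by Wilcoxon-Mann-Whitney (5.3.2.2.4) |
| HBV DNA as predictor of virologic response or HBsAg clearance | No |
| HBV DNA as predictor of HBV DNA clearance | Yes |
| Genotype as predictor | No |
| Linear regression on HBV DNA and genotype | No |
| Linear regression of HBsAg decline on flares | No |
| Any of these listed in 5.3.17 | No |

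**3. The protocol's literal centre term.** About 80 patients at about 35 centres is 80/35 = 2.3 per centre. I simulated a single-visit ANCOVA with 12 unstratified sentinel patients, an assumed block size of 4, equal or unequal centre sizes, an assumed centre share of variance of 0, 0.1 or 0.2, and 1,000 runs per scenario.

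- Residual degrees of freedom are 80 − 3 = 77 without centre and about 47 to 54 with it.
- About 38% to 39% of enrolling centres hold one arm only.
- The ratio of mean SE with centre to mean SE without it runs from 0.2606/0.2246 = 1.16 (no centre variance, equal sizes) to 0.2242/0.2236 = 1.00 (share 0.2, unequal sizes).
- Type I error without centre is 0.027 to 0.044 over the six scenarios. The Monte Carlo standard error near 0.05 is √(0.05 × 0.95/1000) = 0.007.

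The literal term would not help. Leaving centre out errs, if anything, on the conservative side.

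**4. A pooled-region term.** Three regions cost 3 − 1 = 2 degrees of freedom. I simulated 80 patients, 35 centres, blocks of 4 and 1,500 runs, with the regional share of variance (R²) assumed because neither document gives one.

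| Assumed R² | SE without region | SE with region | Reduction | 1 − √(1 − R²) |
|---|---|---|---|---|
| 0.05 | 0.223 | 0.219 | 1.8% | 2.5% |
| 0.10 | 0.223 | 0.213 | 4.5% | 5.1% |
| 0.20 | 0.222 | 0.200 | 9.9% | 10.6% |

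The simulation follows the analytic value less a small cost for imbalance. At R² = 0 there is no gain and perhaps a slight loss.

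**5. Baseline factors.** Expected responders are 40 × 0.25 + 40 × 0.03 = 10 + 1.2 = 11.2. Even with genotype reduced to two groups, a logistic model with treatment, qHBsAg, HBV DNA and genotype has four coefficients besides the intercept, or 11.2/4 = 2.8 responders per coefficient. A linear model of log10 qHBsAg change with the same terms has 80 − 5 = 75 residual degrees of freedom if all Day 169 values are present.

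**6. Flares.** Protocol Table 1 schedules HBsAg after dosing starts only at Days 85 and 169 within the treatment period. On scheduled samples, loss through Day 169 therefore requires a negative result at both visits. A model of decline can use every patient with a measured change. What it can say about flares depends on how many flares occur, and the documents give no estimate.

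**The case against.** Four objections carry weight.

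- **The changes are allowed.** Protocol 10.6 lets the SAP supersede everything but the primary analysis, and the protocol's wording on covariates and on loss or decline is loose. A reader might infer a protocol breach, but the documents do not support that. What remains is that the changes are unlisted and unexplained.
- **Dropping 35 centre levels is sensible.** Step 3 agrees. A reader might infer inflated false positives or needlessly large standard errors. Neither follows: type I error does not rise, and the literal centre term gives an SE equal to or larger than the SAP's. A precision loss exists only relative to a pooled term, and only if regions differ.
- **Some of the content is kept.** HBV DNA remains for HBV DNA clearance, the qHBsAg MMRM is itself a linear model with baseline qHBsAg, and the ELISpot change is stated openly. It would be wrong to say that the HBV DNA regression is gone altogether, or that every endpoint is affected.
- **Flares may be too few.** Protocol 1.3 reports none in Phase 1, and patients generally enter with normal ALT. With few or none, the linear model is as uninformative as the logistic one. This stands and limits the third item.

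Timing also matters. SAP version 2.0 follows an interim analysis that it describes as not meeting the primary and secondary endpoints, and the study is being terminated. Models added now are post hoc. A reader might suspect that the omissions were made in light of results. The documents do not show when they were made, so that cannot be inferred.

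**Conclusion.** The point holds as a set of undeclared omissions with a modest, inexpensive remedy. It concerns the four viral-marker MMRMs, the virologic-response and HBsAg-clearance regressions, and the flare analysis. It gives no reason to expect false positives.

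The firmest gain is the baseline-factor linear model, with up to 80 continuous changes already scheduled for collection against 11.2 responders at planning rates. The region term is worth roughly 2% to 10% in SE if region explains 5% to 20% of variance, and nothing if it explains none. The flare model is conditional on the number of flares. These sizes rest on the planning rates, complete Day 169 data, and assumed variance shares and block size. In a phase 2 study that the SAP itself calls exploratory, this is worth doing but does not undermine the trial's conclusion.

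**What to change.** 1. **SAP 5.3.2.1:** restore a linear model of log10 qHBsAg change to Day 169 on treatment, baseline log10 qHBsAg, baseline HBV DNA and genotype, pooling sparse genotypes by a stated rule.
2. **SAP 5.3.2.2.3:** add a pooled-region term (for example North America / Europe-UK / Asia-Pacific) in place of about 35 centre levels. State that region stands in for the stratification factor, since this too departs from the protocol.
3. **SAP 5.3.3.14:** restore the linear model of log10 qHBsAg change on flare (yes/no), treatment and baseline log10 qHBsAg, reported only if flares reach a stated minimum number.
4. **SAP 5.3.17:** record each of these with its reason, together with anything still left out, such as logistic regression of response on HBV DNA and genotype. Label models added after the Week 24 unblinded analysis as post hoc.

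The cost is SAP wording, two small linear models, one extra term in the existing MMRMs, two pooling rules and about two degrees of freedom. No new data are needed.

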10. STATISTICS

10.1. General Procedures

Baseline is defined as data collected closest to randomization prior to any study medication dosing. All analyses and summary statistics will be presented by treatment group (HepTcell, placebo).

Descriptive statistics, including the numbers and percentages for categorical variables and the numbers, means, standard deviations, medians, minimums and maximums for continuous variables will be provided by treatment.

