2.3.3 Study treatment

HepTcell or normal saline placebo will be administered by IM injection at intervals of 4 weeks for 6 doses. Doses will be administered on Days 1, 29, 57, 85, 113, and 141 (±2 days for each dose). All study administration data collected at patient level will be presented in patient level listings as well as by visit. This will include missed doses or dose delays information.

If an authorized COVID-19 vaccine has been administered in proximity to a scheduled IP administration, a ±3-day window is allowed for IP dosing. Also, from the second dose, if the patient has experienced an acute illness or temperature > 38°C in the 2 days prior to dosing, the administration of study medication and corresponding visit will be delayed until the illness or fever has resolved.

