4.1 Baseline and demographics characteristics

Baseline was defined as the most recent, non-missing value prior to or on the first study treatment dose date. Demographic data and baseline characteristics will be recorded during Screening. Patients can be re-screened and, in this case, these data at re-screening will be recorded and reassessed.

Specific disease variables are the following: Fibroscan, hepatitis B genotype, HCV, HDV, and HIV tests and HBV serology and viral markers including HBsAg, anti-HBs, HBV DNA, pg-RNA, HBcrAg, HBeAg, HBeAg antibody.

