4.2.2 Secondary Efficacy Endpoint

Proportion of patients achieving serologic clearance of HBsAg on Day 169

A patient is considered to have achieved serologic clearance of HBsAg on Day 169, if HBsAg on Day 169 is below the limit of quantitation (defined as 0.05 IU/mL).

Proportion of patients achieving serologic clearance of HBV DNA on Day 169

A patient is considered to have achieved serologic clearance of HBV DNA (PCR) on Day 169, if HBV DNA (PCR) on Day 169 is below the limit of quantitation (defined as 10 IU/mL).

Changes in qHBsAg, HBV DNA, HBcrAg and pg-RNA levels, Baseline to Days 85 and 169
 Changes in qHBsAg, HBV DNA, HBcrAg and pg-RNA levels from Baseline to Days 85 and 169
 are defined as:

Change of Test from Baseline to Day 85 = Test value [Day 85] – Test value [Baseline];

Change of Test from Baseline to Day 169 = Test value [Day 169] – Test value [Baseline];

where Test correspond to the following quantitative tests:

qHBsAg, HBV DNA and HBV DNA log, HBcrAg (Log U/mL and kU/mL) and pg-RNA

• Change in LPMIX9 IFN-γ Spot Forming Cells (SFC) by ELISpot assay in PBMCs, Baseline to Days 85 and 169

Change in LPMIX9 IFN-γ SFC by ELISpot assay in PBMCs, Baseline to Days 85 and 169 are defined as:

Change of LPMIX9 IFN-γ SFC from Baseline to Day 85 = LPMIX9 IFN-γ SFC [Day 85] – LPMIX9 IFN-γ SFC [Baseline];

Change of LPMIX9 IFN-γ SFC from Baseline to Day 169 = LPMIX9 IFN-γ SFC [Day 169] – LPMIX9 IFN-γ SFC [Baseline]

Where LPMIX9 is a pool of the 9 peptides contained in FP-02.2. Values for analyses are LPMIX9 raw values corrected with the control.

- Change in LPMIX9 IFN-γ Spot Forming Cells (SFC) by ELISpot assay in PBMCs:
 - Some replicates of some subjects and days, the -ve Control was higher than the analogous LPMIX9 value which led to negative values.
 - Given that the control does not correspond to the analogous LPMIX9 in each of the replicates since the corresponding wells are not linked, the calculation of the continuous parameter to be analyzed, will be revised as follows:
 - Mean (i=1,2,3) of ["Value for Peptide LPMIX9 (R#i)"] Mean (i=1,2,3) of ["-ve Control for Peptide LPMIX9 (R#i)"] where R#i is replicate #i, i=1,2,3
 - Adding a new specification: If the result turns out negative, it will round up to "0"

Please refer to section 5.3.2 for details on the handling of intercurrent events and missing data or all the secondary endpoints.

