7. APPENDIXES

Appendix 1.- Tables, Figures, and Listings

Appendix 1.- Index of Tables, Figures, and Listings

TFL Number	Title	Analysis Set	Included in	TOP LINE
			Final report	TABLES
Table Number				
14.1 Demograph	ic Data Summary Tables			
14.1.1 Patient Di	sposition			
14.1.1.1	Patient Enrollment and Disposition	All Screened Patients	Yes	V
14.1.1.2	Patient Study Status	All Screened Patients	Yes	
14.1.1.3	Analysis Populations	Randomized Patients	Yes	
14.1.1.4	Protocol Deviations	mITT Population	Yes	
14.1.2 Demograp	phic and Baseline Characteristics			
14.1.2.1	Demographic Characteristics	mITT Population	Only mITT	V
14.1.2.2	Baseline Characteristics	mITT Population	Only mITT	V
14.1.2.3	Specific Disease Characteristics: Fibroscan,	mITT Population	Only mITT	
	Hepatitis B genotype, HCV, HDV and HIV tests			
	and HBV serology and viral markers			
14.1.2.4	Medical History by System Organ Class and	mITT Population	Yes	
	Preferred Term			
14.1.2.5	Baseline Physical Examination	mITT Population	Yes	
14.1.3 Prior and	Concomitant Medications			,
14.1.3.1	Prior Medication by ATC 1st and 2nd level	Safety Population	Yes	
14.1.3.2	Concomitant Medication by ATC 1st and 2nd level	Safety Population	Yes	
14.1.4 Extent of	Exposure for Investigational Products		'	1
14.1.4.1	Treatment Exposure	Safety Population	Yes	
14.2 Efficacy Da	ta Summary Tables and Figures		'	•

TFL Number	Title	Analysis Set	Included in	TOP LINE
			Final report	TABLES
14.2.1 Primary	Efficacy Endpoint			 
14.2.1.1	Summary of patients achieving Virologic Response	mITT Population	Only mITT	V
	on Day 169			
14.2.1.2	Logistic Regression Analysis for Virologic	mITT Population	Only mITT	V
	Response on Day 169			
14.2.2 Seconda	ry Efficacy Endpoint		•	,
14.2.2.1.1	Summary of patients achieving Serologic	mITT Population	Yes	
	Clearance of HBsAg on Day 169			
14.2.2.1.2	Logistic Regression Analysis for Serologic	mITT Population	Yes	V
	Clearance of HBsAg on Day 169			
14.2.2.2.1	Summary of patients achieving Serologic	mITT Population	Yes	
	Clearance of HBV DNA on Day 169			
14.2.2.2.2	Logistic Regression Analysis for Serologic	mITT Population	Yes	V
	Clearance of HBV DNA on Day 169			
14.2.2.3.1	Summary and change from baseline of qHBsAg,	mITT Population	Yes	
	HBV DNA, HBcrAg and pg-RNA levels: Days 85			
	and 169			
14.2.2.3.2	Repeated Measured Mixed Model for qHBsAg,	mITT Population	Yes	
	HBV DNA, HBcrAg and pg-RNA levels: Days 85			
	and 169			

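### The SAP's virology MMRM lists Day 1 among its visits, where change from baseline is zero by definition, so the unstructured model cannot be fitted as written

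*SAP*

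**What the plan says.** SAP 5.3.2.2.3 takes change from baseline in qHBsAg as the response of an MMRM "including treatment group, visits days (Day 1 through Day 169), and baseline values as a covariate". It adds a visit-by-treatment interaction, an unstructured within-patient covariance and REML estimation. HBV DNA, HBcrAg and pg-RNA are to be handled in the same way.

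Three other places fix what a Day 1 change is:

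- SAP 4.1 sets baseline as the "most recent, non-missing value prior to or on the first study treatment dose date".
- SAP 2.3.3 gives the dosing days: "Doses will be administered on Days 1, 29, 57, 85, 113, and 141". The first dose date is therefore Day 1.
- Protocol Table 1 schedules the viral markers at Screening, Day 1, Day 85 and Day 169.

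Elsewhere the SAP uses two response visits. Section 4.2.2 defines change for Days 85 and 169 only, for example "Change of Test from Baseline to Day 169 = Test value [Day 169] – Test value [Baseline". The heading of 5.3.2.2.3 names the same two days. So does Table 14.2.2.3.2 in Appendix 1, whose title begins "Repeated Measured Mixed Model for qHBsAg". The MMRM in protocol 10.4.2 names no Day 1 level.

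**The concern.** In an MMRM of change from baseline, the response vector normally holds post-baseline visits only, and baseline enters as a covariate. Here Day 1 is placed in the visit factor and baseline is also listed as a covariate. The Day 1 response is then a constant, and an unstructured covariance cannot accommodate a response with no variance.

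Protocol 10.6 lets the SAP supersede the protocol on analyses other than the primary one, so this is the operative instruction for four markers. A programmer who follows it literally gets a failed fit, or output that depends on where the optimiser stopped, and must make a repair that the plan does not describe. Some repairs are harmless and some are not. The SAP makes no multiplicity adjustment for these endpoints, so any error in a standard error would pass directly into the reported p-value.

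**Working it through.** The documents give no numerical figure for this model, so there is nothing to reproduce first. The sample-size statement concerns the responder endpoint and does not bear on this point.

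**Step 1: the Day 1 change.** Write Y1 for the Day 1 value, B for baseline and D1 = Y1 − B.

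- If Y1 exists, SAP 4.1 makes B = Y1, so D1 = 0.
- If Y1 is missing, B comes from screening and D1 is missing.

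No patient can have a non-zero D1. This holds on the raw or the log scale.

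**Step 2: the covariance matrix.** For Days 1, 85 and 169, with variances 0, v85 and v169 and with c the covariance of the last two, the rows are (0, 0, 0), (0, v85, c) and (0, c, v169). The determinant is 0 × (v85 × v169 − c²) = 0, whatever the data.

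**Step 3: what REML does.** A simulated data set was fitted with treatment-by-visit means, one common baseline slope and an unstructured covariance. It had 80 patients, 40 per arm; the marker values are assumptions, but the singularity does not depend on them. The three-visit covariance of the changes had rank 2, with eigenvalues 0, 0.0105 and 0.0508. Holding the Day 1 SD at ever smaller values gave:

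| Day 1 SD | −2 REML log-likelihood (up to a constant) | Absolute baseline slope |
|---|---|---|
| 0.1 | −780 | 0.036 |
| 0.01 | −1134 | 0.0035 |
| 0.001 | −1489 | 0.00036 |
| 0.0001 | −1843 | 0.00004 |

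Each tenfold reduction lowers the criterion by 354 to 355. This matches 2 × (80 − 3) × ln 10 = 354.6, where the 3 are the Day 1 intercept, the Day 1 treatment effect and the common slope. The fall has no floor, so there is no finite optimum. The common slope is also driven towards 0, a further sign of degeneracy.

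**Step 4: Days 85 and 169 only.** On the same data the 2 × 2 matrix has full rank (REML eigenvalues 0.0103 and 0.0432). The fit converges from three starting points to one optimum, −425.97, with baseline slope −0.090.

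**Step 5: what each repair would do to the standard errors.**

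- Drop Day 1: no effect on the Day 85 and Day 169 standard errors, 0%.
- Keep Day 1 and use a structure with a separate variance per visit: Day 1 is not pooled with the later visits, so this narrowing does not arise. The zero variance at Day 1 remains.
- Keep Day 1 and use one common variance, with variance s² at both later visits: the pooled variance is (0 + s² + s²)/3 = 2s²/3. The standard error is multiplied by √(2/3) = 0.816, and 1 − 0.816 = 0.184, about 18% too small. Simulated compound-symmetry fits (40 per arm, correlation 0.5 or 0.8, 600 runs per scenario) gave multipliers of 0.815 to 0.819. By the normal approximation a nominal 5% test would then reject in 2 × [1 − Φ(1.96 × 0.816)] = 11.0% of null cases.

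**The case against.** The strongest reply is that Days 85 and 169 were plainly intended. The change formulas, the section heading and the table title all say so, and the Day 1 to Day 169 span can be read as the period supplying the data, with Day 1 as covariate. This stands as a reading of intent, and a careful programmer would probably act on it. It does not rescue the sentence, which puts Day 1 in the visit factor, crosses that factor with treatment, and names baseline separately as the covariate.

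A second reply is that the document history shows no trouble. SAP version 2.0 reports that the Week 24 interim analysis had been done. It dropped the ELISpot MMRM, which has the same visit wording, because of skewness and many zeros, not because of a singular fit, and it kept the virology model. The addendum's list of supplementary tables omits Table 14.2.2.3.2, although the index still marks it for the final report. This suggests that Day 1 was left out in practice, but does not prove it.

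A third reply uses the protocol's baseline wording: "Baseline is defined as data collected closest to randomization prior to any study medication dosing". Randomization may precede Day 1 by up to 3 working days, so a screening value could be baseline for some patients and their Day 1 change could be non-zero. The SAP definition governs the SAP model, however, and it excludes this.

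Finally, these are unadjusted secondary analyses in a study that the SAP describes as exploratory. The primary analysis is untouched. The SAP also reports that the primary and secondary endpoints were not met, so no positive claim rests on this model. All of that stands and limits the weight of the point.

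**Conclusion.** The model specification is wrong as written: with Day 1 as a response visit it cannot be estimated, and it contradicts the SAP's own endpoint definitions. That conclusion follows from the definitions alone and needs no assumption about the data.

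The practical size is small. Four secondary analyses are affected, and the natural repair, omitting Day 1, introduces no bias.

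A reader might infer that these models failed, or that the reported error bars are about 18% too narrow. The documents support neither. They record no failed fit and name no fallback covariance. The 18% needs three conditions together: Day 1 retained, a common-variance structure in place of the unstructured one, and equal variances at Days 85 and 169. The supportable range is 0% to about 18%, with 0% if the SAP's own formulas were followed.

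**What to change.** In SAP 5.3.2.2.3, replace the Day 1 to Day 169 span with Days 85 and 169 as the response visits, and state that baseline enters only as the covariate. The matching sentence for ELISpot in 5.3.2.2.4 should be aligned for consistency, although that model has been replaced by a Wilcoxon-Mann-Whitney test.

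Confirm that the programs for qHBsAg, HBV DNA, HBcrAg and pg-RNA used these two visits. State in the report which visits and which covariance structure were fitted. If Day 1 was included, rerun the models without it and say so.

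The cost is a few words of text and one program check; no new data are needed.
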